2.0 BACKGROUND**Introduction**

Historically the management of localized adenocarcinoma of the prostate has followed a monotherapy strategy. (1, 2) For several decades, patients thought to have organ-confined prostate cancer or minimal risk of extracapsular disease were offered either radical prostatectomy or radical irradiation. Although these therapies are considered curative, it is well recognized that the potential for cure is highly dependent on stage and grade. Approximately 30% of patients with organ-confined prostate cancer and up to 60% of patients with T3 tumors are at risk for a systemic relapse despite curative intent radical prostatectomy. (3) The figure is higher if the nodes are positive.

In patients with clinically organ confined prostate cancer, freedom from biochemical relapse at 5 years is related to Gleason score, PSA, pathologic T and N stage and status of the surgical margin. (4 - 8) Freedom from relapse at 5 years ranging from 83% - 95% is especially associated with Gleason score of ≤ 6, pT1-T2 with a pre-therapy PSA of < 10 ng/ml. (5) A preoperative PSA of > 20 ng/ml, poorly differentiated histology (Gleason ≥ 8), seminal vesicle or extensive surgical margin involvement or nodal metastases define a high risk group of patients with a 50% or greater biochemical relapse rate at 5 years. (5 - 8) These data suggest the presence of occult systemic disease at time of initial diagnosis underscoring the potential importance of early systemic therapy. The case for the latter may be strengthened by the knowledge that recurrent/metastatic prostate cancer is currently incurable in the majority of cases.

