6.0 STRATIFICATION FACTORS/RANDOMIZATION SCHEME

- 6.1 At the time of registration, patients will be randomly assigned to either Arm 1 or Arm 2 according to a dynamic allocation scheme. The treatment arms will be balanced with respect to the following factors:
- a. Pathologic stage of disease:
 1. organ confined (pT2a - pT2b with either ± surgical margins), but N0,
 2. not organ confined (\geq pT3), but N0,
 3. N1 (any T).
 - b. Gleason's sum: < 7, 7, > 7.
 - c. RT planned: Yes vs. No.

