10.0 CRITERIA FOR EVALUATION AND ENDPOINT DEFINITIONS

- 10.1 Overall Survival: Measured from date of randomization to date of death from any cause. Patient known to be alive are censored at date of last contact.
- 10.2 Disease-Free Survival: Measured from date of randomization to date of first observation of recurrence or death due to any cause. Patients without recurrence are censored at date of last contact.
- 10.3 **Performance Status:** Patients will be graded according to the current Southwest Oncology Group grading scale:
- | GRADE | SCALE |
|---------------------|---|
| 0 | Fully active; able to carry on all predisease activities without restriction. |
| 1 | Restricted in physically strenuous activity but ambulatory and able to carry out work of a light or sedentary nature, e.g., light housework, office work. |
| 2 | Ambulatory and capable of all self-care but unable to carry out any work activities. Up and about more than 50% of waking hours. |
| 3 | Capable of only limited self-care; confined to bed or chair more than 50% of waking hours. |
| 4 | Completely disabled. Cannot carry on any self-care. Totally confined to bed or chair. |
| 5 | Dead |
- 10.4 PSA Progression: A serum PSA level of > 0.2 ng/mL measured on 3 consecutive occasions or in the absence of increasing PSA, a positive bone scan result or other radiographic or histologic evidence of progression will be used. Date of progression will be the date that the first measure of increasing PSA is noted in the series of 3. (40)
- 10.5 PSA Progression-Free Survival: Measured from date of randomization to date of PSA progression or death due to any cause.

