11.0 STATISTICAL CONSIDERATIONS

- 11.1 The primary objective of this study is to compare the overall survival in prostate cancer patients treated with combined androgen blockade (LHRH agonist and anti-androgen) with that in patients treated with the combination of combined androgen blockade and mitoxantrone plus prednisone. Mitoxantrone, prednisone and combined androgen blockade would be judged superior to the standard regimen of combined androgen blockade if the true increase in median survival is 30%.
- 11.2 It was initially anticipated that 250 eligible patients per year would be accrued to this study. However, accrual has been slower than expected. Instead of the original accrual period estimate of 5.5 years, we now anticipate a period of 9.5 years in order to randomize 680 eligible patients per arm.
- 11.3 A median survival of 10 years is anticipated on combined androgen blockade. Assuming exponential survival, 9.5 years of patient accrual, and an additional 4 years of follow-up, a sample size of 680 patients per arm, this study has .92 power to detect a 30% increase in median survival, using a one-sided test with 0.05 significance level.
- 11.4 This study will be monitored throughout the accrual and follow-up periods by the Southwest Oncology Group Data and Safety Monitoring Committee (DSMC). The DSMC will be approved by CTEP and will include members both from within the Group and from outside the Group. A majority of the DSMC will be outside members, and at least one outside member will be a patient advocate and at least one will be a statistician. The

Group Statistician and two representatives of CTEP will be non-voting members. The Group Chair may not be on the DSMC. The DSMC will be provided with administrative reports every 6 months by the Study Statistician, and will discuss the reports if necessary at a meeting held in conjunction with the Southwest Oncology Group Meeting. The DSMC and study statistician will be the only individuals with regular access to the primary outcome data and this information will be provided to the DSMC on a regular basis.

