- 11.5 In addition to the study monitoring mentioned above, three formal interim analyses will be done. The decision to terminate accrual early will be made by the DSMC, and will consider disease-free survival, toxicities, and other factors in addition to survival. Additionally, the Southwest Oncology Group Statistical Center will closely monitor throughout the trial whether there is differential use of optional radiotherapy between the two treatment groups and this information will be provided to the DSMC at regular intervals.
- 11.6 The first formal interim analysis will be done after 700 patients have been entered, approximately 6 years after the study opens. Evidence suggesting early termination of the trial would be if the alternative hypothesis of a 30% improvement in survival with the MP + CZ combination arm is rejected at the 0.005 level, using an extension of the logrank test that allows for testing a relative risk not equal to 1. In addition, the null hypothesis of no difference in survival will be tested at the one-sided level of 0.005. The second interim analysis will be performed after 50% of the total expected deaths (275 deaths) will have occurred. Testing will be done as above at the 0.005 level. A third interim analysis will be performed 2.5 years after accrual has been completed. This testing will also be done at the alpha=0.005 level. The final analysis will be performed at the 0.045 significance level, approximately 4 years after accrual has been completed.
- 11.7 Secondary analyses will also be done regarding disease-free survival and toxicities. With 680 patients per arm, toxicity rates can be estimated to within at \pm 4% (95% confidence interval).

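### Section 11 does not specify the survival tests as stratified by the factors that balance the arms; stratifying by stage and Gleason sum would recover about 0 to 1.5 points of power under weak to moderate prognostic effects

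*Combined protocol and SAP*

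**What the plan says.** Section 6.1 describes dynamic allocation and states: "The treatment arms will be balanced with respect to the following factors". The factors are pathologic stage (3 levels), Gleason sum (3 levels) and planned radiotherapy (yes or no). The Registration Form has a field for each.

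The primary endpoint, overall survival, is defined in Section 10.1: "Measured from date of randomization to date of death from any cause".

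Section 11 covers the survival tests as follows.
- **11.3, power.** The calculation assumes exponential survival and mentions no factors, "using a one-sided test with 0.05 significance level".
- **11.6, test of the 30% alternative.** This is done "using an extension of the logrank test that allows for testing a relative risk not equal to 1", with no strata mentioned.
- **11.6, interim null test.** Only the level is given: "the null hypothesis of no difference in survival will be tested at the one-sided level of 0.005".
- **11.6, final test.** Again only the level: "The final analysis will be performed at the 0.045 significance level".
- **11.5.** The one related variable in Section 11 is a monitoring item, "differential use of optional radiotherapy between the two treatment groups". That is radiotherapy actually given, not the planned radiotherapy of Section 6.1.

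**The concern.** When arms are balanced on factors that predict outcome and the test ignores them, two things follow. The balance makes the test statistic vary less than the unstratified logrank variance assumes, so the true one-sided error falls below its nominal level. Mixing patients of different risk also pulls the unstratified treatment effect toward no difference. Both act against a true benefit, and neither inflates false positives.

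There is also a question of pre-specification. With the final test unnamed, someone must later choose whether to stratify and by which of three factors, possibly after outcomes are known.

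The documents give some reason to expect prognostic value. Section 2.0 says that "freedom from biochemical relapse at 5 years is related to Gleason score, PSA, pathologic T and N stage", although that concerns biochemical relapse. The same section gives five-year survival for Gleason 8-10 patients in a trial of adjuvant hormonal therapy with radiotherapy.

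**Working it through.** **1. Reproduce the stated power (Section 11.3).** Inputs: control median 10 years, experimental median 13, accrual 9.5 years, further follow-up 4 years, 680 per arm, one-sided 0.05. Uniform accrual and no dropout are assumed.

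P(death) = 1 − [exp(−4λ) − exp(−13.5λ)] / (9.5λ)
- Control, λ = ln 2/10 = 0.0693: 0.445 × 680 = 302.5 deaths.
- Experimental, λ = ln 2/13 = 0.0533: 0.366 × 680 = 249.0 deaths.
- Total 551.4, which agrees with 275 being half of the expected deaths in Section 11.6.

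Schoenfeld: √(551.4/4) × ln 1.3 = 3.08. Subtracting 1.645 gives 1.436, so power is .924 (stated .92). At 0.045, subtracting 1.695 gives 1.385 and power .917.

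**2. What the documents imply about Gleason score and survival.** For the radiotherapy trial, Section 2.0 gives five-year survival of 55% (control) and 66% (adjuvant) in Gleason 8-10, against 71% and 75% overall. The Gleason 8-10 share s is not given; 20% to 40% is assumed.

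Survival in the rest = (overall − s × Gleason 8-10) / (1 − s); hazard ratio = ln(Gleason 8-10) / ln(rest)
- Control: s = .2 gives rest .750, HR 2.08; s = .4 gives rest .817, HR 2.95.
- Adjuvant: s = .2 gives rest .772, HR 1.61; s = .4 gives rest .810, HR 1.97.

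The range is about 1.6 to 3.0, in a different population.

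**3. Simulated power at the final one-sided 0.045.** In both set-ups there are 1,360 patients, the overall control median is 10 years and the within-cell HR is 1/1.3. The cost of the interim looks is not modelled. The mixes and prognostic effects are assumptions.

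Set-up A: stage .25/.50/.25, Gleason .10/.50/.40, planned radiotherapy .35, marginal minimisation with a 0.8 biased coin, 60,000 trials per case. The same effect applies to each step of stage and of Gleason sum. Half unrelated means that half of the mean hazard is the same in every cell.

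| Effect per level | Power, unstratified | Power, 9 cells | Gain, points | Type I error, unstratified | Type I error, 9 cells |
|---|---|---|---|---|---|
| None | .916 | .914 | −0.2 | .045 | .045 |
| HR 1.25 | .914 | .915 | 0.1 | .044 | .045 |
| HR 1.5, half unrelated | .914 | .914 | 0.1 | .045 | .046 |
| HR 2, half unrelated | .909 | .914 | 0.6 | .043 | .046 |
| HR 1.5 | .905 | .917 | 1.2 | .040 | .045 |
| HR 2 | .882 | .920 | 3.8 | .033 | .046 |

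Set-up B: stage .20/.55/.25, Gleason .15/.45/.40, exact balance within cells, 8,000 to 15,000 trials per case.

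| Hazards by level | Power, unstratified | Power, 9 cells | Gain, points |
|---|---|---|---|
| 1/1.2/1.5 on both | .913 | .915 | 0.2 |
| 1/1.5/2.0 on both | .914 | .921 | 0.7 |
| Gleason >7 only, 1.75 | .916 | .921 | 0.5 |
| Gleason >7 only, 2.4 | .900 | .916 | 1.6 |
| 1/1.5/2.5 on both | .901 | .915 | 1.4 |
| 1/1.75/3 on both | .895 | .917 | 2.2 |
| Gleason 1/1.3/3.0, stage 1/1.5/2.5 | .891 | .917 | 2.6 |
| 1/2/4 on both | .878 | .919 | 4.1 |

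A large-sample calculation that gives no credit for balanced allocation yields larger gains (0.5 to 0.6 point at 1/1.2/1.5, and 6.2 to 7.5 at 1/2/4). The trial does balance, so the simulations are the better guide.

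**4. Planned radiotherapy as a further factor (18 cells).** It adds nothing under set-up A. With no prognostic factor, power is .912 against .914 for 9 cells. With HR 1.5, half unrelated, and radiotherapy itself prognostic, 9 against 18 cells gives .914 and .910 (radiotherapy HR 1.25) or .913 and .911 (HR 1.5).

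**5. Sparse cells.** Nine cells keep 97.8% of the logrank information at 127 deaths, 98.5% at 275, and 98.9% to 99.0% at the third look and the final analysis.

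**The case against.** The strongest reply is that nothing in Section 11 is wrong. The plan is silent on stratification, its power figure reproduces, and every gain above depends on mixes and hazard ratios that the documents do not give. All of that stands, and it is why the point is minor.

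Three practical objections also have some force.
- **Source of the strata.** Section 6.1 does not say whether the Gleason sum comes from biopsy or surgical specimen, and the Prestudy form records both. That form also allows NX, while the strata offer only N0 or N1. Using the Registration Form fields settles which value enters the analysis, because those fields drove the allocation. It does not settle how sites filled them in.
- **Two of three factors.** Leaving planned radiotherapy out of the primary strata is a judgement supported only by simulation. Hence the sensitivity analysis.
- **Timing.** The closure notice reports a monitoring committee analysis on January 10, 2007, and 488 patients on the chemotherapy arm. A change can reach only the analyses still to come.

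Stronger readings are tempting. A reader might infer that the plan prescribes an unstratified test; it does not, because the interim null test and the final test are not named. A reader might infer inflated false positives; the simulated error of the unstratified test is at or below .045 in every case. A reader might infer a loss of several points of power. That needs strong effects of both factors: HR 2 per level of each implies control medians by cell from 52 down to 3.3 years, which is hard to believe.

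In the other direction, it would be wrong to say that the documents hold no survival figures by Gleason score. Section 2.0 does, for other patients. The weaker prognostic cases in set-up A (gains of 0.1 to 0.6 point) correspond to a Gleason >7 hazard ratio of only 1.26 to 1.48, below the implied 1.6 to 3.0. A ceiling of 1 point would therefore be too low.

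**Conclusion.** The point holds as a minor, inexpensive improvement. The arms are balanced on three factors, no survival test is specified as stratified by them, and two of the three kinds of test are not named.

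If the gap is filled by an unstratified logrank test, the loss against a test stratified by stage and Gleason sum is about 0 to 1.5 points of power under weak to moderate effects and about 2 to 4 points under strong ones. These ranges rest on the assumed stage and Gleason mixes, the assumed hazard ratios and proportional hazards within cells. The Gleason range implied by Section 2.0 comes from radiotherapy patients and an assumed 20% to 40% share of Gleason 8-10. The figures describe the planned design of 1,360 patients and are not estimates for the closed trial. Patients are still followed for up to 15 years (Section 7.9), so the final comparison still needs a named test.

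**What to change.** In Section 11.6, state that the overall survival tests still to be done, including the final test, are one-sided logrank tests stratified by pathologic stage (3 levels) and Gleason sum (3 levels), using the values in the stratification fields of the Registration Form. State that the hazard ratio comes from a Cox model with the same 9 strata. Pre-state one sensitivity analysis that adds planned radiotherapy (18 cells). A short note should say which Gleason sum the registration field holds and how NX patients were classified.

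The cost is a few sentences and no new data. If the factors are not prognostic, the 9-cell test gives up about 0.2 point of power; the 18-cell analysis would give up about 0.4. The text should be fixed before anyone choosing the test sees further survival results by arm.

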12.0 DISCIPLINE REVIEW

There will be no discipline review for this study.

13.0 REGISTRATION GUIDELINES

- 13.1 Patients must be registered prior to initiation of protocol treatment (no more than ten working days prior to planned start of treatment).
- 13.2 For either phone or web registration, the individual registering the patient must have completed the appropriate Southwest Oncology Group Registration Form. The completed form must be referred to during the registration but should not be submitted as part of the patient data.

The individual registering the patient must also be prepared to provide the treating institution's name and ID number in order to ensure that the current (within 365 days) date of institutional review board approval for this study has been entered into the data base. Patients will not be registered if the IRB approval date has not been provided or is > 365 days prior to the date of registration.

13.3 Registration Procedures

- a. You may register patients from Member, CCOP, UCOP and approved Affiliate institutions to a therapeutics study using the SWOG Registration program. To access the Registration program go to the SWOG Web site (<http://swog.org>) and click on the *Logon* link to go to the SWOG Members Area logon page (<https://swog.org/visitors/logon.asp>). This Web program is available at any time except for periods listed **under Down Times**. Log on as an Individual User using your SWOG Roster ID Number and individual web user password. Help for the logon process may be found at <https://swog.org/visitors/logonhelp.asp>. After you have logged on, click on the *Clinical Trials* link and then the *Patient Reg* link to go to the Entry Page for the Patient Registration program. If you are a Registrar at an institution with Internet access you are encouraged to register this way. For new users, the link to a "Starter Kit" of help files may be found by clicking on **Starter Kit link at the logon page**.

To register a patient the following must be done (in order):

1. You are entered into the Southwest Oncology Group Roster and issued a SWOG Roster ID Number,
2. You are associated as an investigator or CRA/RN to the institution where a registration is occurring, and
3. You are granted permission to use the Patient Registration program at that institution.

For assistance with points 1 and 2 call the SWOG Operations Office at [name]. For point 3 you must contact your Web User Administrator. Each SWOG institution has one or more Web User Administrators who may set up Web Users at their institution and assign permissions and passwords to these users. For other password problems or problems with the Patient Registration program, please e-mail [contact]. Include your name, Roster ID Number, and telephone number, when the problem occurred, and exactly what you were doing.

4. If the Web Reg program is not used, the registration must be done by phone.

Member, Affiliate, CCOP, and UCOP Institutions

Registration by phone of patients from member, affiliate and CCOP institutions must be done through the Southwest Oncology Group Data Operations Center in Seattle by telephoning [name], 6:30 a.m. to 4:00 p.m. Pacific Time, Monday through Friday, excluding holidays.

- 13.4 **CALGB Institutions:** Confirm all eligibility criteria as listed in Section 5.0. Registration will be accepted through institutions with direct registration privileges. Call the CALGB Registrar ([name], Monday - Friday, 9:00 AM - 4:30 PM, Eastern Time) with the following information:

Study

Name of Group (CALGB)
Name of institution where patient is being treated
Name of treating physician
Naming of treating physician or responsible CRA
CALGB patient ID#, if applicable
Patient's first name, middle initial, and last name
Patient's Social Security number, date of birth and hospital ID number
Patient's gender
Patient's height, in centimeters
Patient's weight, in kilograms
Patient's race
CTC performance status (optional, if required by CDUS)
Type of insurance (method of payment)
Disease, type and stage, if applicable
Patient's Postal Code, if applicable
Treatment start date
Date of signed consent
Eligibility criteria met (yes, no)
Stratification factors (Surgical extent of disease, Gleason Sum, RT planned; see Section 6.1)

The CALGB Registrar will then contact the Southwest Oncology Group Statistical Center for treatment assignment, after which the CALGB Registrar will inform the institution of the treatment assignment. The Southwest Oncology Group will forward a confirmation of treatment assignment to the CALGB Registrar, who will subsequently forward the confirmation of treatment assignment to the main member institution.

Patients entered on this study may not be cancelled (see Section 13.6).

13.5 **CTSU REGISTRATION/RANDOMIZATION**

Prior to the recruitment of a patient for this study, investigators must be registered members of the CTSU. Each investigator must have an NCI investigator number and must maintain an "active" investigator registration status through the annual submission of a complete investigator registration packet (FDA Form 1572 with original signature, current CV, Supplemental Investigator Data Form with signature, and Financial Disclosure Form with original signature) to the Pharmaceutical Management Branch, CTEP, DCTD, NCI. These forms are available on the CTSU registered member Web site or by calling the PMB at [contact] Monday through Friday between 8:30 a.m. and 4:30 p.m. Eastern time.

Each CTSU investigator or group of investigators at a clinical site must obtain IRB approval for this protocol and submit IRB approval and supporting documentation to the CTSU Regulatory Office before they can enroll patients. Study centers can check the status of their registration packets by querying the Regulatory Support System (RSS) site registration status page of the CTSU member web site at <http://members.ctsu.org>.

All forms and documents associated with this study can be downloaded from the **S9921** Web page on the CTSU registered member Web site (<https://members.ctsu.org>). Patients can be registered only after pre-treatment evaluation is complete, all eligibility criteria have been met, and the study site is listed as 'approved' in the CTSU RSS.

Requirements for S9921 site registration:

- CTSU IRB Certification
- CTSU IRB/Regulatory Approval Transmittal Sheet

Prestudy requirements for patient enrollment on S9921

- Patient must meet all inclusion criteria, and no exclusion criteria should apply
- Patient has signed and dated all applicable consents and authorization forms
- All baseline laboratory tests and prestudy evaluations performed.

CTSU Procedures for Patient Enrollment

1. Contact the CTSU Patient Registration Office by calling [name]. Leave a voicemail to alert the CTSU Patient Registrar that an enrollment is forthcoming. For immediate registration needs, e.g. within one hour, call the registrar cell phone at [name].
 2. Complete the following forms:
 - CTSU Patient Enrollment Transmittal Form
 - Eligibility Criteria Checklist (Section 5.0 of the protocol)
 - SWOG Registration Form (Complete all sections of form except for SWOG-specific data fields)
 3. Fax these forms to the CTSU Patient Registrar at [name] between the hours of 8:00 a.m. and 8:00 p.m., Mon-Fri, Eastern Time (excluding holidays). The CTSU registrar will check the investigator and site information to ensure that all regulatory requirements have been met. The registrar will also check that forms are complete and follow-up with the site to resolve any discrepancies.
 4. Once investigator eligibility is confirmed and enrollment documents deemed complete, the CTSU registrar will contact the Southwest Oncology Group to obtain assignment of a treatment arm and assignment of a unique patient ID (to be used on all future forms and correspondence). The CTSU registrar will convey this information to the enrolling site and follow up with a confirmation via e-mail or fax.
- 13.6 For either method of registration, exceptions to Southwest Oncology Group registration policies will not be permitted.
- a. Patients must meet all eligibility requirements.
 - b. Institutions must be identified as approved for registration.
 - c. Registrations may not be cancelled.
 - d. Late registrations (after initiation of treatment) will not be accepted.

